9.2 Recording of Adverse Events

At each contact with the subject, the study team must seek information on adverse events by specific questioning and, as appropriate, by examination. Information on all adverse events should be recorded immediately in the source document, and also in the appropriate adverse event section of the case report form (CRF). All clearly related signs, symptoms, and abnormal diagnostic, laboratory or procedure results should be recorded in the source document.

All adverse events occurring during the study period must be recorded. The clinical course of each event should be followed until resolution, stabilization, or until it has been ultimately determined that the study treatment or participation is not the probable cause. Serious adverse events that are still ongoing at the end of the study period must be followed up, to determine the final outcome. Any serious adverse event that occurs during the Adverse Event Reporting Period and is considered to be at least possibly related to the study treatment or study participation should be recorded and reported immediately.

9.3 Reporting of Serious Adverse Events and Unanticipated Problems

When an adverse event has been identified, the study team will take appropriate action necessary to protect the study participant and then complete the Study Adverse Event Worksheet and log. The sponsor-investigator will evaluate the event and determine the necessary follow-up and reporting required.

9.3.1 Sponsor-Investigator reporting: notifying the Mayo IRB

The sponsor-investigator will report to the Mayo IRB any UPIRTSOs and Non-UPIRTSOs according to the Mayo IRB Policy and Procedures.

Action taken regarding treatment

AE Action:

All adverse events should be treated appropriately. Treatment may include one or more of the following:

- No action taken (i.e. further observation only)
- [study/investigational] treatment dosage adjusted/temporarily interrupted
- [study/investigational] treatment permanently discontinued due to this adverse event
- concomitant medication given
- non-drug therapy given
- patient hospitalized/patient's hospitalization prolonged

AE Outcome:

- All AE outcomes should be recorded (not recovered/not resolved; recovered/resolved; recovering/resolving, recovered/resolved with sequelae; fatal; or unknown)

Serious Adverse Events (SAE)

An SAE is defined as any adverse event (appearance of (or worsening of any pre-existing) undesirable sign(s), symptom(s) or medical conditions(s) which meets any one of the following criteria (Life-threatening in the context of a SAE refers to a reaction in which the patient was at risk of death at the time of the reaction; it does not refer to a reaction that hypothetically might have caused death if more severe.):

- Is fatal or life-threatening
- Results in persistent or significant disability/incapacity
- Constitutes a congenital anomaly/birth defect
- Requires inpatient hospitalization or prolongation of existing hospitalization, unless hospitalization is for:
 - Routine treatment or monitoring of the studied indication, not associated with any deterioration in condition (specify what this includes)
 - Elective or pre-planned treatment for a pre-existing condition that is unrelated to the indication under study and has not worsened since signing the informed consent
 - Treatment on an emergency outpatient basis for an event not fulfilling any of the definitions of a SAE given above and not resulting in hospital admission
 - Social reasons and respite care in the absence of any deterioration in the patient's general condition
- Is medically significant, i.e. defined as an event that jeopardizes the patient or may require medical or surgical intervention.

SAE Reporting:

To ensure patient safety, every SAE, regardless of causality, occurring after the patient has provided informed consent and until 30-days after the subject stopped study participation must be reported to the Incyte as soon as possible but no later than 5 days from learning of its occurrence according to the Mayo Clinic IRB policy. Any SAEs experienced after the 30-days period should only be reported to Incyte and the Mayo Clinic IRB if the investigator suspects a causal relationship to study treatment. Recurrent episodes, complications, or progression of the initial SAE must be reported as follow-up to the original episode, regardless of when the event occurs. This report must be submitted as soon as possible but no later than 5 days from the investigator receiving the follow-up information. SAE should be followed up until resolution or until it is judged to be permanent. An SAE that is considered completely unrelated to a previously reported one should be reported separately as a new event.

Information collected on the adverse event worksheet (*and entered in the research database*):

- Subject's name:
- Medical record number:
- Disease/histology (if applicable):
- The date the adverse event occurred:
- Description of the adverse event:
- Relationship of the adverse event to the research (drug, procedure, or intervention*):
- If the adverse event was expected:
- The severity of the adverse event: (use a table to define severity scale 1-5**)
- If any intervention was necessary:

- Resolution: (was the incident resolved spontaneously, or after discontinuing treatment)
- Date of Resolution:

AE Reporting:

Its relationship to the:

- Study treatment (no/yes), or
- Investigational treatment (no/yes), or
- The other study treatment (non-investigational) (no/yes), or
- Both or indistinguishable

The relationship will be categorized as follows:

- Unrelated- Clearly due only to extraneous causes, and does not meet criteria listed under possible or probable.
- Unlikely- Does not follow a reasonable temporal sequence from administration. May have been produced by the patient's clinical state or by environmental factors or other therapies administered.
- Possible- Follows a reasonable temporal sequence from administration, but may have been also produced by the patient's clinical state, environmental factors or other therapies administered.
- Probable- Clear-cut temporal association with administration with improvement on cessation of investigational medicinal product or reduction in dose. Reappears upon rechallenge. Follows a known pattern of response to the investigational medicinal product.

Its duration (start and end dates) or if the event is ongoing an outcome of not recovered/not resolved should be reported.

Whether it constitutes a serious adverse event(SAE)

Adverse Events (AE):

The severity grade/Common Toxicity Criteria (CTC) AE Version 4.0 grade

- Mild: usually transient in nature and generally not interfering with normal activities
- Moderate: sufficiently discomforting to interfere with normal activities
- Severe: prevents normal activities

If CTCAE grading does not exist for an adverse event, use

1=mild, 2=moderate, 3=severe, 4=life-threatening, CTCAE Grade 5 (death) is not used, but is collected in other CRFs (Study Completion, Death/Survival).

9.3.2 Sponsor-Investigator reporting: Notifying the FDA and Funding Sponsor

The sponsor-investigator will report to the FDA all unexpected, serious suspected adverse reactions according to the required IND Safety Reporting timelines, formats and requirements.

Unexpected fatal or life threatening suspected adverse reactions where there is evidence to suggest a causal relationship between the study drug/placebo and the adverse event, will be reported as a serious suspected adverse reaction. This will be reported to the FDA on FDA Form 3500A, no later than 7 calendar days after the sponsor-investigator's initial receipt of the information about the event.

Other unexpected serious suspected adverse reactions where there is evidence to suggest a causal relationship between the study drug/placebo and the adverse event, will be reported as a serious suspected adverse reaction. This will be reported to the FDA on FDA Form 3500A, no later than 15 calendar days after the sponsor-investigator's initial receipt of the information about the event.

Any clinically important increase in the rate of serious suspected adverse reactions over those listed in the protocol or product insert will be reported as a serious suspected adverse reaction. This will be reported to the FDA on FDA Form 3500A no later than 15 calendar days after the sponsor-investigator's initial receipt of the information about the event.

Findings from other studies in human or animals that suggest a significant risk in humans exposed to the drug will be reported. This will be reported to the FDA on FDA Form 3500A, no later than 15 calendar days after the sponsor-investigators initial receipt of the information about the event.

SAE Reporting to the Sponsor (Incyte)

All Serious Adverse Events ("SAE") required to be reported pursuant to the Protocol shall be provided to Incyte and its representatives by Institution or Principal Investigator within twenty-four (24) hours of learning of the event as well as provide any additional reports agreed upon by the Institution or Principal Investigator and Incyte's contact below. SAE Reports will be sent to the email address provided below. By sending to this e-mail address, the Incyte Pharmacovigilance group and the Incyte clinical operations project manager will receive copies of the reports. This process will be tested and established before the first patient is enrolled in the trial. Notwithstanding anything to the contrary herein, Institution or Principal Investigator will have the primary responsibility of reporting adverse events ("AE") to regulatory authorities.

Copies of IND safety reports submitted to the FDA by the Institution will be shared with the contact below so that these reports can be evaluated and included in investigator brochure or Incyte IND safety submissions as required to ensure safety of other patients who are receiving the product from Incyte for sponsored trials.

Incyte Corporation: [REDACTED] for e-mail transmission of individual SAE reports.

Safety Contacts: [REDACTED], Exec. Dir, Incyte Pharmacovigilance, Phone: [REDACTED]
[REDACTED] Email: [REDACTED]

Procedure for Reporting of Pregnancy and Lactation to the Sponsor (Incyte)

Data on fetal outcome are collected for regulatory reporting and drug safety evaluation. Follow-up should be conducted for each pregnancy to determine outcome, including spontaneous or voluntary termination, details of the birth, and the presence or absence of any birth defects, congenital abnormalities, or maternal and/or newborn complications.

Within 30 days of learning of the pregnancy, the investigational site completes the Clinical Trial Pregnancy Form (sections I, II, and question 18 in section III) or equivalent, and e-mails the report to Incyte at [REDACTED]

Within 30 days of learning of the outcome of the pregnancy (delivery, termination, or miscarriage), the investigational site completes the Clinical Trial Pregnancy Form (sections II, III, IV, and V) or equivalent, and e-mails the report to Incyte at [REDACTED]

NOTE: If a woman has a positive pregnancy test at Baseline, the investigational site completes Clinical Trial Pregnancy Form (sections I, II, and III (question 18)) or equivalent and e-mails the report to Incyte at [REDACTED] as per established timelines.

Any SAE occurring during pregnancy must be reported to Incyte as an SAE, in accordance with Section 3 of the Serious Adverse Event Reporting Plan, as provided by Incyte.

9.4 Stopping Rules

The stopping rules specified below are based on the knowledge available at study development. The stopping rule applies to the overall study. We note that the Adverse Event Stopping Rule may be adjusted in the event of either (1) the study re-opening to accrual or (2) at any time during the conduct of the trial and in consideration of newly acquired information regarding the adverse event profile of the treatment(s) under investigation. The study team may choose to suspend accrual because of unexpected adverse event profiles that have not crossed the specified rule below.

Accrual will be temporarily suspended to this study if at any time we observe events considered at least possibly related to study treatment (i.e. an adverse event with attribute specified as “possible”, “probable”, or “definite”) that satisfy the following:

- If 2 or more patients in the first 6 treated patients (or 30% after the first 6 treated patients have been accrued) experience a grade 3 or higher non-hematologic adverse event.

We note that we will review grade 4 and 5 adverse events deemed “unrelated” or “unlikely to be related”, to verify their attribution and to monitor the emergence of a previously unrecognized treatment-related adverse event.

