2.4 Clinical Data to Date

INCB018424 PHOSPHATE CREAM has been evaluated in over 200 subjects with plaque psoriasis in 3 clinical studies with dosing of 1 to 3 months' duration.

Study INCB 18424-201 was a double-blind, vehicle-controlled, rising-dose, safety, tolerability, PK, and preliminary efficacy study of INCB01824 1% cream applied QD and 1.5% cream applied BID. All doses were safe and well tolerated. Preliminary efficacy was consistently shown for the 1.0% QD and 1.5% BID cohorts compared with vehicle, with a trend toward a dose response. The 1.5% cream BID showed similar responses compared with Dovonex® (calcipotriene) 0.005% cream and Diprolene® AF (betamethasone dipropionate) 0.05% cream. Systemic bioavailability of INCB018424 was independent of formulation strength. All adverse events (AEs) were mild to moderate in intensity and most judged unrelated to study medication, with no associated serious AEs (SAEs) or withdrawals. Laboratory and ECG evaluations did not suggest any safety issues, specifically no instances of neutropenia, thrombocytopenia, or leukopenia.

INCB 18424-202 was an open-label, multicenter, sequential-cohort, dose-escalation, safety, tolerability, PK, pharmacodynamic (PD), and preliminary efficacy study of INCB018424 PHOSPHATE CREAM 1.0% or 1.5% applied to 2% to 20% BSA QD or BID for 4 weeks. Application area increased sequentially, and alternative dosing paradigms were explored at the highest application area. The efficacy analyses collectively demonstrated efficacy of all 5 regimens of INCB018424 PHOSPHATE CREAM in psoriasis. The incidence of all reported AEs, the clinical laboratory results, vital signs, and ECG findings showed no confirmed safety signals or trends. Mean topical bioavailability ranged from 3.4% to 5.2% with no significant inhibition of cohort mean PD. Overall, INCB018424 PHOSPHATE CREAM (1.0% or 1.5%) was demonstrated to be safe and well tolerated when applied QD or BID for 28 days to plaque psoriasis affecting 2% to 20% of the BSA.

INCB 18424-203 was a double-blind, randomized, multicenter, parallel group, vehicle-controlled dose-ranging study with application of INCB018424 PHOSPHATE CREAM or vehicle in subjects with stable plaque psoriasis. The study was designed to evaluate safety and efficacy of INCB018424 PHOSPHATE CREAM 0.5%, 1.0%, or 1.5% relative to vehicle cream when applied QD for 12 weeks in equal size groups.

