INCB018424 has also been administered orally as single or multiple doses to healthy volunteers and subjects with inflammatory, hematologic, and oncologic disease. Oral administration has been generally safe and well tolerated. Literature reports also indicate that oral INCB018424 may restore hair growth in patients with alopecia areata.

INCB018424 PHOSPHATE CREAM appears to pose a low risk of cutaneous toxicity. INCB018424 PHOSPHATE CREAM applied at concentrations $\leq 1.5\%$ (10 mg/cm² application rate to 10% BSA corresponding to 434-1099 cm²) was well tolerated in a 9-month assessment in the Gottingen minipig. INCB018424 PHOSPHATE CREAM did not act as a contact sensitizer nor did it produce significant dermal irritation or demonstrate phototoxicity or photoallergenic potential. This lack of adverse cutaneous effects has been supported by clinical trials to date where cutaneous AEs have been infrequent and of similar frequency and severity as with vehicle control treatment. INCB018424 PHOSPHATE CREAM tested positive in a photoclastogenicity assay; hence there may be a risk of skin reaction to the combined exposure of INCB018424 PHOSPHATE CREAM and sunlight. Subjects should be cautioned to avoid excessive exposure to either natural or artificial sunlight (including tanning booths, sun lamps, etc), and, when outdoors, should be advised to wear loose-fitting clothing that protects the treated area from the sun.

The primary clinical risks noted with orally administered INCB018424 treatment are the potential sequelae of decreased hematopoietic proliferation secondary to the inhibition of growth factor pathways by JAK2 antagonism. Systemic exposure with topical INCB018424 PHOSPHATE CREAM is several fold below that which is associated with hematologic changes that may be seen following oral dosing. Dose-dependent, reversible thrombocytopenia has been

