2.6 Risks and Benefits

Benefits:

Others with LP may benefit in the future from what we learn in this research study. It is possible their symptoms could also improve while being treated with this study drug

Risks:

The following adverse events were reported as very common Side effects associated with the use of INCB018424 PHOSPHATE CREAM:

- Occurring in greater than or equal to 10% of subjects), common (occurring in 1-10% of subjects), and rare (occurring in 0.1% of subjects) side effects occurring in 203 subjects with psoriasis treated with INCB018424 PHOSPHATE CREAM up to 1.5% twice daily strength (the highest strength to be used in this study) in 3 previous studies. Additionally, 54 subjects with alopecia areata (immune-related condition of hair loss) are participating in an ongoing study.

Very Common (affecting more than 10 in every 100 patients)
No adverse event was seen in more than 10% of the psoriasis subjects treated with INCB018424 PHOSPHATE CREAM up to 1.5% twice daily

•

Common (affecting less than 10 in every 100 patients)	
Upper respiratory tract infection/nasopharyngitis (common cold)	Abdominal pain (stomach pain)
Application site irritation (irritation on skin where study treatment is applied)	Muscle strain
Headache	Throat Pain
Change in ECG tracing	Psoriasis (skin disorder under treatment)
Pruritus (itching)	Blood sugar increased
Sinusitis (sinus infection)	Cholelithiasis (stone in gall bladder)
Back Pain	Cough
Diarrhea	Cystitis (irritation of bladder)
Dry Skin	Skin redness
Liver enzyme increased	Bulging disk in back
Gastroenteritis (vomiting/diarrhea caused by virus)	Blood cell count decreased
	Pneumonia (lung infection)
	Fever
	Skin peeling

Common (affecting less than 10 in every 100 patients)	
Influenza (flu)	Toothache

Rare but Serious
In seven out of 203 patients treated, serious adverse events were observed but were considered unrelated to INCB018424 PHOSPHATE CREAM use. Due to the number of patients studied to date, rare serious adverse events cannot be predicted with any certainty.

Photosensitivity:

There may be a risk of skin reaction to the combined exposure of INCB018424 PHOSPHATE CREAM and sunlight.

Hematologic abnormalities:

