INCB018424 taken systemically can inhibit the growth of blood cells. Low blood cells can make subjects more susceptible to infections by bacteria, virus, and fungi. The risk is low with systemic therapy and was not noted with topical therapy but subjects will be monitored for any signs of inhibition of their blood counts.

Infection risk:

There is a theoretical increase in risk of infection with topical use of INCB018424 PHOSPHATE CREAM. This will be monitored for.

INCB018424 may increase risk of infections and reactivation of latent infections such as Tuberculosis or Valley Fever. Serious bacterial, fungal and viral infections were observed in patients receiving INCB018424. Please seek medical advice if signs or symptoms suggestive of infection occur.

Allergy:

It is possible that some people could have an allergic reaction to INCB018424 PHOSPHATE CREAM.

Cancer Risk:

INCB018424 PHOSPHATE CREAM may have the potential to affect subject's immune system; they may be at increased risk for infections and possibly cancer. Live vaccines should not be given concurrently with INCB018424 PHOSPHATE CREAM.

Pregnancy Risk:

The effect of the study drug on a fetus (developing baby still in the womb), or on a breastfeeding infant, is unknown and may be harmful. Because of these risks, women cannot take part in this study if they are pregnant or breastfeeding.

Skin biopsy:

A skin biopsy is generally a safe procedure, but some potential risks may include local pain, mild local bruising, bleeding, scarring, and an infection at the site where the skin biopsy was performed. If a topical antibiotic is used afterwards, then there is a small risk of an allergic reaction.

Chest X-ray:

Subjects will be exposed to radiation from the chest x-ray. The amount of radiation has a low risk of harmful effects.

Blood draw:

The risks of drawing blood include pain, bruising, lightheadedness, and/or fainting, or rarely, infection at the site of the needle stick.

Other:

As with all research, there is a chance that confidentiality could be compromised; however, we take precautions to minimize this risk.

3 Study Objectives

Primary Objective:

To determine the efficacy of INCB018424 PHOSPHATE CREAM as measured by the change in Modified CAILS score of the index treatment and control lesion (weeks 0 and 4) and changes in lesion count (week 0 and 4)

Secondary Objective:

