Individuals will then initiate treatment on all lesions of LP BID and will be evaluated weekly and assessed by PGA, BSA, lesion count; Modified CAILS, Pruritus NRS, and Skindex-16 between weeks 0-4 (see Appendix). Week 4 will be the primary endpoint; however therapy will be continued for an additional 4 weeks. Therapy will be stopped and the individuals will be evaluated at week 8 and assessed by PGA, BSA, lesion count, Modified CAILS, Pruritus NRS, and Skindex-16. Laboratory and safety monitoring will occur at weeks 1, 2, 3, 4, and 8, and 12. 3D Photographs will be taken at weeks 0, 1, 2, 3, 4, 8, and 12. Individual lesions will be circled at that time and the exact volume of each lesion will be measured. Up close photos will be taken of the disease and normal tissues attained at weeks 0 & 4.

Tissue will be collected for RNA sequencing at week 0 and 4. Blood collection will include the isolation at week 0, 2, and week 4, 5mL vials of blood which will be separated and the serum and cell pellet will be stored for future analysis. Five skin biopsies will be taken during the study. At week 0, up to two 3mm tissue biopsies will be taken from lesional skin and one biopsy will be taken from normal appearing skin. The initial biopsy of lesional tissue and control will be

annotated. At week 4, up to two 3mm biopsies will be taken from lesional responsive tissue and lesional refractory tissue. Responsive and non-responsive lesions will be determined by the change in Modified CAILS between week 0 and 4. Responsive will require a 50% reduction in Modified CAILS and non-responsive can have progression, no change, or up to a 50% reduction in Modified CAILS. The lesions will be chosen using full body photographs taken at week 0. Up to 60 samples will be snap frozen and stored in the tissue biobank. Once completed, RNA sequencing will be performed on the 60 tissue samples and analysis will be performed. Paired analysis of treatment responsive and refractory lesions will be made as well as treated and untreated lesions.

Nucleic Acid Extractions: RNA will be extracted from a total of 50 um of fresh tissue using the Qiagen FFPE RNeasy Micro extraction Kit according to manufacturer's recommendation.

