4.3 Duration of Participation

The study consists of 3 epochs: screening/washout period (of at least 1 week and up to 4 weeks), treatment epoch (of 8 weeks from screen/washout), and follow up epoch (of 4 weeks). The screening and washout period will allow for treatment naïve/ new diagnosis LP to undergo evaluation and diagnosis and for treatment refractory to undergo a washout. The total duration of the study will be 13-16 weeks.

Tables:

• **Table-1: Prohibited treatment**

Prohibited treatments^{†, ‡}	Washout period (before Randomization Visit)
Any concomitant oral or topical JAK inhibitor	Prohibited
Any biologic drug	Stable dose for 3 months
Immunomodulation treatments for LP [§] [e.g., methotrexate, cyclosporine A, corticosteroids (oral, i.v., intramuscular, s.c., intra-articular, transdermal), mycophenolate mofetil, azathioprine]	4 weeks
Topical treatment that is likely to impact signs and symptoms of LP (e.g., pimecrolimus, tacrolimus)	2 weeks
Non-immunosuppressive agents (tetracycline antibiotics & niacinamide)	2 weeks
Prohibited regimen of Topical Corticosteroids (TCS)	
TCS on any location on body (including face, scalp and/or genitoanal area)	2 weeks

[†] If the prohibited treatment is being used during the study for any indication, the subject must discontinue use of the prohibited treatment if he/she wishes to continue in the study.

[‡] In case of undue safety risk for the subject, the subject should discontinue study treatment at the discretion of the investigator/qualified site staff. If the subject received a live virus vaccination during the study, the subject must discontinue study treatment.

[§]Inhalative CS with only a topical effect (e.g., to treat asthma) are not considered “systemic immunomodulation treatments” and are therefore acceptable as co-medication. Immunosuppressive medication for conditions other than LP will be allowed.

Table-2: Screening and Visits (+/- 2 day window)

	Screening	Day 0	Week 1	Week 2	Week 3	Week 4	Week 8	Week 12

INCB18424		X	X	X	X	X		
Physical Exam	X	X	X	X	X	X	X	X
Adverse Event Assessment		X	X	X	X	X	X	X
Chest X-ray	X							
Assessments: PGA, BSA, lesional number, Modified CAILS, Skindex-16, Pruritus NRS		X	X	X	X	X	X	X
Photographer		X	X	X	X	X	X	X
Skin Biopsy (tissue/serum bank)		X				X		
Urine Pregnancy Test	X							
Venipuncture	X	X	X	X	X	X	X	X
Biomarker/RNAseq blood (tissue/serum bank)		X		X		X		
CMP	X		X	X	X	X	X	X
CBC	X		X	X	X	X	X	X
Quantiferon Gold	X							
Hepatitis B	X							
Hepatitis C	X							

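### Section 9.4's only mandatory accrual-suspension rule excludes hematologic events, so related grade 3 or higher cytopenias can pause accrual only at the team's discretion; a one-word change is optional

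*Combined protocol and SAP*

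**What the plan says.** **The rule.** Section 9.4 makes temporary suspension of accrual mandatory under one condition only: that 2 or more of the first 6 treated patients, or 30% once those 6 are in, "experience a grade 3 or higher non-hematologic adverse event" rated at least possibly related to treatment. No hematologic counterpart appears in 9.4, in 9.5 or in the Supplementals. The same section lets the team suspend for an unexpected adverse event profile that has not crossed the rule. It also lets the rule itself be changed at any time in light of new adverse event information.

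**Blood-count monitoring.** Section 4.1 states "Laboratory and safety monitoring will occur at weeks 1, 2, 3, 4, and 8, and 12", and the CBC row of Table-2 agrees, with a further CBC at screening. That is six post-baseline draws. The last falls four weeks after the end of treatment.

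**Hematologic risk.** Section 2.4 gives reduced blood-cell production, through JAK2 inhibition, as the primary clinical risk of the oral drug. For the cream it says "Systemic exposure with topical INCB018424 PHOSPHATE CREAM is several fold below that which is associated with hematologic changes". It also reports, for study 201 (which included 1.5% BID), "specifically no instances of neutropenia, thrombocytopenia, or leukopenia". Section 2.6 says of the hematologic risk that it "was not noted with topical therapy but subjects will be monitored for any signs of inhibition of their blood counts". The table of common side effects in the same section nevertheless lists "Blood cell count decreased", without grade or attribution.

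**The concern.** The trial measures blood counts at every scheduled visit after Day 0 because the drug class can suppress them, but its one study-level rule is worded so that suppression cannot count. Two related grade 3 or higher non-hematologic events among the first 6 patients pause accrual automatically. Two related grade 3 or higher cytopenias in the same patients leave the decision to judgement, and section 9.4 does not say why the two classes are treated differently.

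The gap is narrower than the wording first suggests. A cytopenia that leads to a related grade 3 or higher infection still counts, because the infection is a non-hematologic event. What escapes is a severe related cytopenia with no such consequence.

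The stake is whether a temporary pause in accrual of a 12-subject study is automatic or discretionary. Endpoints and estimates are not affected.

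**Working it through.** The plan gives no operating characteristics for the rule, so there is no stated figure to reproduce.

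**Inputs from the documents**
- Threshold (section 9.4): 2 or more of the first 6, then 30%.
- Sample size (section 4.2): 12.
- Patients needed under the 30% part: 0.30 × 7 = 2.1 and 0.30 × 10 = 3.0, so 3 patients for n = 7 to 10. Then 0.30 × 11 = 3.3 and 0.30 × 12 = 3.6, so 4 patients for n = 11 and 12.

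**Assumed inputs**
- Per-patient probability p of a related grade 3 or higher cytopenia: 1%, 2%, 5% and 10%. The documents give no rate. Section 2.6 says "No adverse event was seen in more than 10% of the psoriasis subjects" treated with the cream, but that describes psoriasis subjects on strengths up to 1.5% BID. It makes 10% a convenient upper illustration, not a bound for this trial.
- Patients are independent, and each outcome is counted in order of treatment.

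**As written.** Cytopenias alone trigger the rule with probability 0, whatever the rate.

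**With hematologic events counted, first 6 patients**

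P6 = 1 − (1 − p)^6 − 6p(1 − p)^5

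At p = 0.05: 1 − 0.73509 − 0.23213 = 0.0328.

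**With hematologic events counted, all 12 patients.** If the first 6 show 0 or 1 event, the rule can still be crossed by reaching 3 at n ≤ 10, or by having 2 at n = 10 and events in both of the last two patients. At p = 0.05 the added terms are:
- 0 in the first 6, then at least 3 of the next 4: 0.73509 × 0.00048 = 0.00035
- 1 in the first 6, then at least 2 of the next 4: 0.23213 × 0.01402 = 0.00325
- exactly 2 after 10 patients without an earlier crossing, then two more: 0.04976 × 0.0025 = 0.00012

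Sum: 0.03277 + 0.00035 + 0.00325 + 0.00012 = 0.0365.

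| Assumed cytopenia rate | As written | Counted: first 6 | Counted: all 12 |
|---|---|---|---|
| 1% | 0 | 0.15% | 0.15% |
| 2% | 0 | 0.6% | 0.6% |
| 5% | 0 | 3.3% | 3.7% |
| 10% | 0 | 11.4% | 13.6% |

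A crossing reached only with the twelfth patient leaves no accrual to pause, so the last column slightly overstates the practical effect.

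**Total chance of a pause after the change.** Assume a 5% related non-hematologic rate and an independent hematologic rate h. The pooled rate is q = 1 − 0.95(1 − h), which is 5.95%, 6.9% and 9.75% for h = 1%, 2% and 5%. Putting q into the same formulas:

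| Added hematologic rate | First 6 | All 12 |
|---|---|---|
| none (as written) | 3.3% | 3.7% |
| 1% | 4.5% | 5.1% |
| 2% | 5.9% | 6.8% |
| 5% | 10.9% | 13.0% |

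**The case against.** The strongest reply is that the exclusion fits the evidence and other provisions cover the event.

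**Evidence.** Section 9.4 says its rules rest on what was known when the study was developed. For the cream, that knowledge is reassuring: lower systemic exposure, no cytopenias in study 201, and no confirmed laboratory signal in study 202 at 2% to 20% BSA over 4 weeks. This stands, and it is why the event is treated here as unlikely. A reader might infer from the common side-effect listing that severe cytopenia is to be expected. Without grade or attribution, the listing does not support that.

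**Other safeguards.** A reader might infer that the trial cannot stop for hematologic toxicity. The documents do not support that either:
- The team may suspend for unexpected profiles. Section 9.1, writing about UPIRTSO reporting, treats greater than expected frequency or severity as unexpected. Two related grade 3 or higher cytopenias in 6 patients would plausibly qualify, although that definition was not written for section 9.4.
- The rule may be adjusted at any time on new adverse event information.
- Section 9.5 requires regular assessment of serious adverse events in aggregate, though it sets no threshold and covers only serious events.
- Laboratory review, interruption or discontinuation of the cream, and reporting to the IRB, the FDA and the funder apply patient by patient.

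All of this stands. None of it makes suspension automatic for a cytopenia.

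**Patient protection.** A reader might also infer that patients already on treatment are left exposed. They rely on the CBCs and on stopping the cream; a pause in accrual does not act on them.

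**False alarms.** Table-1's footnote says "Immunosuppressive medication for conditions other than LP will be allowed", and the attribution scale in section 9.3.1 rates an event possible even when other therapies may have caused it. A background cytopenia could therefore count. This stands in part. It is limited by the screening CBC, by the section 9.1 rule that a preexisting condition is an adverse event only if it worsens, and by the Supplemental 3 rule that a laboratory abnormality is an adverse event only if it causes symptoms, is clinically significant or needs therapy.

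**Conclusion.** The point holds as a minor one. The only mandatory suspension criterion cannot be met by related grade 3 or higher cytopenias that have no grade 3 or higher non-hematologic consequence, although blood-count suppression is the oral drug's primary risk and is monitored at six post-baseline visits. Suspension for such events is possible but discretionary.

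The practical size is small. At the 1% to 5% rates that fit the topical data better, counting cytopenias would produce a cytopenia-only pause in under 4% of 12-patient trials. The change matters mainly if the true rate is unexpectedly high. All these percentages rest on assumed rates, on independence between patients, and on reading the 30% part as 3 of 7 to 10 and 4 of 11 to 12. The finding that cytopenias alone cannot trigger the rule rests on the wording of section 9.4 and needs none of these assumptions.

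**What to change.** Optional: delete the word non-hematologic from the criterion in section 9.4, so that any at least possibly related grade 3 or higher adverse event counts toward the existing threshold. This is simpler than a separate cytopenia criterion, because it needs no new threshold, grading rule or data; the CBCs are already scheduled.

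The cost is a somewhat higher chance of a temporary pause, as in the second table, including an occasional pause driven by background cytopenia in a subject on a permitted immunosuppressant. If the sponsor prefers to keep the exclusion, one sentence in section 9.4 giving the reason would be enough.
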